11.1.2.1 Evaluation of Target Lesions

Unfortunately the Histiocyte Society does not specify what constitutes radiographic regression or progression of disease. Since histiocyte disorders are hematologic malignancies we will use modified Cheson criteria to assign response as outlined below.

Response	Definition	Nodal Masses	Spleen and Liver	Bone Marrow
CR	Disappearance of all evidence of disease	 (a) FDG-avid or PET positive prior to therapy; mass of any size permitted if PET negative (b) Variably FDG-avid or PET negative; regression to normal size on CT 	Not palpable, nodules disappeared	Infiltrate cleared on repeat biopsy; if indeterminate by morphology, immunohistochemistry should be negative
PR	Regression of measurable disease and no new sites	 ≥50% decrease in SPD of up to 6 largest dominant masses; no increase in size of other nodes (a) FDG-avid or PET positive prior to therapy; one or more PET positive at previously involved site (b) Variably FDG-avid or PET negative; regression on CT 	≥50% decrease in SPD of nodules (for single nodule in greatest transverse diameter); no increase in size of liver or spleen	Irrelevant if positive prior to therapy
SD	Failure to attain CR/PR or PD	 (a) FDG-avid or PET positive prior to therapy; PET positive at prior sites of disease and no new sites on CT or PET (b) Variably FDG-avid or PET negative; no change in size of previous lesions on CT 	Any but PD below	Any but PD below
PD	Any new lesion or increase by _ 50% of previously involved sites from nadir	Appearance of a new lesion(s) > 1.5 cm in any axis, ≥ 50% increase in SPD of more than one node, or ≥50% increase in longest diameter of a previously identified node > 1 cm in short axis Lesions PET positive if FDG-avid lymphoma or PET positive prior to therapy	>50% increase from nadir in the SPD of any previous lesions	New or recurrent involvement

Deauville Criteria for PET scan interpretation in lymphoma will be used in this study as outlined below:

Five-point scale:

1. No Uptake

2. Uptake \leq mediastinum

3. Uptake >mediastinum but \leq liver

4. Uptake moderately increased compared to liver at any site

5. Uptake markedly increased compared to the liver at any site or/and new sites of disease

A score of 1-3 is PET NEGATIVE. A score of 4-5 is PET POSITIVE.

11.1.2.2 Evaluation of skin lesions

Skin lesions are not always detectable by PET/CT or other radiographic techniques. Skin lesions will be assessed by direct measurement. Photographs are encouraged but not required. Responses in skin are outlined below:

Complete resolution: no detectable skin abnormality Regression: 50% or greater reduction in the sum of the cumulative area of skin lesions Stable: not fulfilling criteria for resolution, regression, or progression Progression: new skin lesions (biopsy confirmation preferred but not mandatory) or 50% increase in area of at least one skin lesion

11.1.2.3 Evaluation of Best Overall Response

The best overall response is the best response recorded from the start of the treatment until disease progression/recurrence (taking as reference for progressive disease the smallest measurements recorded since the treatment started). The patient's best response assignment will depend on the achievement of both measurement and confirmation criteria. Responses should be maintained for at least 8 weeks. If a patient has multiple sites of disease and any of these sites are active the patient is considered to have a best overall response of active disease.

11.1.3 Duration of Response

Duration of overall response: The duration of overall response will be measured from the time measurement criteria are met for CR or PR (whichever is first recorded) until the first date that recurrent or progressive disease is objectively documented (taking as reference for progressive disease the smallest measurements recorded since the treatment started, or death due to any cause. Participants without events reported are censored at the last disease evaluation).

Duration of overall complete response: The duration of overall CR will measured from the time measurement criteria are first met for CR until the first date that progressive disease is objectively documented, or death due to any cause. Participants without events reported are censored at the last disease evaluation.

Duration of stable disease: Stable disease will be measured from the start of the treatment until the criteria for progression are met, taking as reference the smallest measurements recorded since the treatment started, including the baseline measurements.

11.1.4 Progression-Free and Overall Survival

Overall Survival: Overall Survival (OS) is defined as the time from randomization (or registration) to death due to any cause, or censored at date last known alive.

Progression-Free Survival: Progression-Free Survival (PFS) is defined as the time from randomization (or registration) to the earlier of progression or death due to any cause. Participants alive without disease progression are censored at date of last disease evaluation.

11.1.5 Response Review

Radiology will be centrally reviewed by the DF/HCC Tumor Imaging Metrics Core (TIMC) and the treating clinician will add clinical data (e.g., status of skin lesions not assessable by radiology) as appropriate.

12. DATA REPORTING / REGULATORY REQUIREMENTS

Adverse event lists, guidelines, and instructions for AE reporting can be found in Section 7.0 (Adverse Events: List and Reporting Requirements).

12.1 Data Reporting

12.1.1 Method

The QACT will collect, manage, and perform quality checks on the data for this study.

12.1.2 Responsibility for Data Submission

Investigative sites within DF/HCC or DF/PCC are responsible for submitting data and/or data forms to the QACT according to the schedule set by the QACT.

12.2 Data Safety Monitoring

The DF/HCC Data and Safety Monitoring Committee (DSMC) will review and monitor toxicity and accrual data from this study. The committee is composed of clinical specialists with experience in oncology and who have no direct relationship with the study. Information that raises any questions about participant safety will be addressed with the Overall PI and study team.

The DSMC will review each protocol up to four times a year or more often if required to review toxicity and accrual data. Information to be provided to the committee may include: up-to-date

participant accrual; current dose level information; DLT information; all grade 2 or higher unexpected adverse events that have been reported; summary of all deaths occurring with 30 days of intervention for Phase I or II protocols; for gene therapy protocols, summary of all deaths while being treated and during active follow-up; any response information; audit results, and a summary provided by the study team. Other information (e.g. scans, laboratory values) will be provided upon request.

12.3 Multicenter Guidelines

N/a

12.4 Collaborative Agreements Language

N/A

13. STATISTICAL CONSIDERATIONS

13.1 Study Design/Endpoints

The primary endpoint of this study is to evaluate the overall response rate of lenalidomide in patients with LCH. This is a pilot study with a planned accrual of 12 patients. A small sample size was selected due to the rarity of the disease and the difficulty in accruing a larger number of patients at a single center.

Study treatment will be considered worthy of further evaluation if at least three (25%) of 12 patients experience a response. The 90% exact binomial confidence limits for three responses in 12 patients is 7-53%. We will consider a response rate of 5% unworthy of further study for this patient population, and note that two responses in 12 patients is the maximum number of responses which still includes the unworthy response rate of 5% in its confidence limits.

The limited sample size may cause us to miss a small but potentially clinically meaningful response rate or to overestimate the response rate. We are willing to accept this in order to complete the trial in a reasonable time period while recognizing that the results of this trial will be used to determine whether a larger phase II trial of lenalidomide is warranted in which case such a trial would be proposed to the Histiocytosis Society.

Secondary endpoints will include:

- Duration of response
- Progression free survival

- Overall survival
- Description of toxicity
- Quantitative serial measurements of urine and plasma cell free DNA for BRAF mutation as a biomarker of response
- Quantitative serial measurements of serum TNF-alpha levels as a biomarker of response

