1.2 Primary Objectives

To estimate the response rate of patients with relapsed/refractory ECD, LCH, and HS with single agent lenalidomide.

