1.3 Secondary Objectives

- To define the progression free survival (PFS) after treatment with lenalidomide
- To define the overall survival (OS) after treatment with lenalidomide
- To describe the safety profile of lenalidomide in LCH, ECD, and HS
- To assess quantitative changes in urinary and plasma cell free DNA harboring the BRAF V600E mutation and correlate the presence or absence of the BRAF V600E mutation with response
- To assess serial changes in TNF-alpha levels in patients treated with lenalidomide
- To assess the mutational landscape of these diseases using Oncopanel

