3.1 Eligibility Criteria

- 3.1.1 Patients must have histologically or cytologically confirmed LCH, ECD or HS. Confirmation of outside pathology at BWH will be performed but is not mandatory prior to study enrollment (see section 3).
- 3.1.2 Detectable disease by at least one of the following modalities: CT, PET, bone scan, or MRI.
- 3.1.3 Patients with LCH must require systemic therapy according to the Histiocyte Society LCH Evaluation and Treatment Guidelines (HS 2009) Or Patients with HS requiring systemic treatment as defined by disease that cannot be surgically resected and/or encompassed in a single radiation field.
- 3.1.4 Age 18 years or older.
- 3.1.5 ECOG performance status ≤ 2 (Karnofsky $\geq 60\%$, see Appendix A)
- 3.1.6 Participants must have normal organ and marrow function as defined below:

_	absolute neutrophil count	≥1,000/mcL
_	platelets	≥100,000/mcL
-	total bilirubin	within 1.5 times normal institutional limits
-	AST(SGOT)/ALT(SGPT)	$\leq 3 \times$ institutional upper limit of normal
-	creatinine	within 2 times normal institutional limits
		OR
-	creatinine clearance	\geq 30 mL/min/1.73 m ² . Note, dose adjustments are
		required for $CrCl \ge 30$ mL/min but ≤ 60 ml/min.

- 3.1.7 Able to take aspirin 81 mg daily as prophylactic anticoagulation if not on warfarin, low molecular weight heparin or oral factor Xa inhibitor. Patients intolerant to ASA may use warfarin or low molecular weight heparin at doses designed to treat deep venous thrombosis.
- 3.1.8 All study participants must be registered into the mandatory Revlimid REMS® program, and be willing and able to comply with the requirements of the REMS® program.

- 3.1.9 Women of child-bearing potential and men must agree to use adequate contraception (hormonal or barrier method of birth control; abstinence) prior to study entry and for the duration of study participation.
- 3.2.0 Ability to understand and the willingness to sign a written informed consent document.

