11. MEASUREMENT OF EFFECT

11.1 Definitions

Evaluable for toxicity: All participants who receive at least one dose of study treatment will be evaluable for toxicity from the time of their first treatment.

Evaluable for objective response: Any patient who receives at least one dose of lenalidomide will be considered evaluable for response. These participants will have their response classified according to the definitions stated below. Patients not evaluable for response will not be replaced by another protocol participant.

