13.2 Sample Size, Accrual Rate and Study Duration

The planned accrual is 12 patients. The estimated accrual is 5 patients per year so we anticipate the accrual will occur over a 2 to 2.5 year period. Up to an additional 6 months of follow-up will be required on the last participant accrued to assess response. Thus the total study duration is anticipated to be 2.5 to 3 years.

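### Section 13.1 states the primary endpoint for LCH alone, but the rule of 3 responses in 12 fits the pooled accrual of LCH, ECD and HS, so a pooled pass could be read as an LCH result

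*Combined protocol and SAP*

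**What the plan says.** Section 13.1 defines the endpoint: "The primary endpoint of this study is to evaluate the overall response rate of lenalidomide in patients with LCH". It gives the decision rule, "Study treatment will be considered worthy of further evaluation if at least three (25%) of 12 patients experience a response", and the reference rate, "We will consider a response rate of 5% unworthy of further study for this patient population". LCH is the only disease that 13.1 names, so on its face the 5% rate belongs to LCH. The section adds that the 90% exact limits for 3/12 are 7-53%, and that 2/12 is the largest count whose limits still include 5%.

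Other sections describe a wider group:

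- Section 1.2, primary objective: "To estimate the response rate of patients with relapsed/refractory ECD, LCH, and HS with single agent lenalidomide".
- Section 1.3, safety objective: "To describe the safety profile of lenalidomide in LCH, ECD, and HS".
- Section 3.1.1, eligibility: "Patients must have histologically or cytologically confirmed LCH, ECD or HS".
- Section 11.1: "Any patient who receives at least one dose of lenalidomide will be considered evaluable for response".
- Section 13.5 counts as a responder an eligible and evaluable participant who meets the response definition. Section 13.7.2 assesses every treated participant, even after major treatment deviations. Neither names a disease.
- Section 13.2: "The planned accrual is 12 patients". No section sets a minimum number with LCH, says that all 12 must have LCH, or says that ECD and HS patients are enrolled on top of the 12. No analysis by disease is specified.

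**The concern.** The rule in 13.1 is the trial's only efficacy go/no-go criterion, and 13.1 says that the result will determine whether a larger phase II trial is warranted. The population attached to that rule therefore decides what the trial may conclude.

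Read alone, 13.1 describes an LCH trial. Read with the rest of the plan, it describes a trial of three diseases with one pooled count. If responses come largely from ECD or HS patients, the rule can be met while the LCH data say little, and the wording of 13.1 would then attach the pass to LCH. Leaving the population open until responses are known would also allow it to be chosen with the answer in view.

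**Working it through.** **Inputs.** From 13.1: 12 patients, at least 3 responses, unworthy rate 5%, two-sided 90% exact binomial limits. From 13.2: total accrual 12. The number of LCH patients is not given, so all possible values are considered.

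**Step 1: reproduce the plan's figures.** The exact (Clopper-Pearson) lower limit L for x responses in n solves P(X ≥ x | n, L) = 0.05. The upper limit U solves P(X ≤ x | n, U) = 0.05.

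| Responses | 90% limits | Includes 5%? |
|---|---|---|
| 2/12 | 3.0-43.8% | yes |
| 3/12 | 7.2-52.7% | no |

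As a direct check, the lower limit exceeds 5% exactly when P(X ≥ x | n, 0.05) is below 0.05.

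- P(X ≥ 2 | 12, 0.05) = 1 − 0.5404 − 0.3413 = 0.118, so 2/12 does not exclude 5%.
- P(X ≥ 3 | 12, 0.05) = 1 − 0.5404 − 0.3413 − 0.0988 = 0.0196, so 3/12 does.

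The stated 7-53% and the 2/12 boundary are both correct for a denominator of 12.

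**Step 2: who makes up the 12?** Under 3.1.1, 11.1, 13.2 and 13.7.2 the 12 are the treated patients of all three diseases. They are 12 LCH patients only if nobody with ECD or HS enrols, which no section requires.

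**Step 3: can the pooled rule pass without three LCH responses?** Let m be the number of LCH patients, with 12 − m others.

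- m = 1: 1 LCH response and 2 among the other 11 make 3. So do 0 and 3.
- m = 2 to 11: 2 LCH responses and 1 among the others make 3.
- m = 12: not possible.

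So it can happen at every LCH count from 1 to 11. For m = 8, with 2 LCH responses and 1 elsewhere, the pooled count is 3/12, a pass. For LCH alone, P(X ≥ 2 | 8, 0.05) = 1 − 0.6634 − 0.2793 = 0.057, which is above 0.05. The 90% limits for 2/8 are 4.6-60.0% and include 5%.

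**Step 4: how often might this matter?** The plan gives no disease mix and no rates by disease, so the following is an illustration under assumed values. Take 6 LCH patients at a true 5% (A responses) and 6 others at a true rate q (B responses), independent. Then

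P(pass) = 1 − [P(A=0)·P(B≤2) + P(A=1)·P(B≤1) + P(A=2)·P(B=0)],

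with P(A=0) = 0.7351, P(A=1) = 0.2321 and P(A=2) = 0.0305.

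| q | P(B≤2) | P(B≤1) | P(B=0) | P(pass) |
|---|---|---|---|---|
| 25% | 0.8306 | 0.5340 | 0.1780 | 0.26 |
| 40% | 0.5443 | 0.2333 | 0.0467 | 0.54 |
| 50% | 0.3438 | 0.1094 | 0.0156 | 0.72 |

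If all 12 patients had a true rate of 5%, the probability would be 0.02 (step 1).

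**Step 5: the reverse case.** Three or more LCH responses always make three or more in total. With the stated count of three kept, a pooled fail together with an LCH pass is therefore impossible at any LCH count.

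**The case against.** The strongest reply is that the plan can be carried out as it stands. It has one accrual, one count and one denominator, and 13.7.2, which deals specifically with the primary efficacy endpoint, takes every treated participant. An analyst would count responders among all treated patients and compare with three, so what is wrong is a phrase in 13.1. This largely stands, and it is why pooling is the better supported reading. It does not remove the contradiction: the section that sets the endpoint and the unworthy rate names a population that the rule does not use.

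Two further points stand. Sections 11.1, 13.5 and 13.7.2 include ECD and HS by not restricting, not by naming them. And the outcomes in step 3 are possibilities; the probabilities in step 4 rest on assumed rates and an assumed even split.

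A reader might infer that the two readings can conflict in both directions, for example that 2 responses in 7 LCH patients with none elsewhere fail 3/12 while the LCH limits (5.3-65.9%) exclude 5%. The documents do not support this. The rule in 13.1 is a count of three, and the interval only explains that cut-off. The reverse conflict appears only if the count is replaced by an interval-only rule.

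A reader might also infer that pooling guarantees a denominator of 12. It does not: 12 is the planned accrual, 11.1 rules out replacement, and 13.5 counts only eligible and evaluable participants.

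**Conclusion.** The concern holds as an inconsistency in the stated primary population. Section 13.1 gives LCH; 1.2 and 3.1.1 give LCH, ECD and HS; and the analysis sections exclude no disease. The numbers in 13.1 are correct and are not in question. As worded, a pooled pass could be taken as an LCH result although it can occur with fewer than three LCH responses at any LCH count from 1 to 11. In the illustration the chance of a pass with LCH at the unworthy rate is 0.26 to 0.72, conditional on the assumed 6/6 split and assumed rates of 25% to 50% in the others. If all 12 patients have LCH, the problem disappears. It should be fixed, and wording is enough.

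The sections also differ on relapsed/refractory status and on any condition for ECD (1, 1.1, 1.2, 3 and 3.1.3). That is a separate eligibility matter which does not affect the 3/12 rule; those passages should be reconciled in their own right.

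**What to change.** Before responses are known:

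1. Amend 13.1 so that the primary endpoint, the 5% rate, the 3/12 rule and the 90% exact interval all apply to treated patients with LCH, ECD or HS (planned n = 12).
2. Make 13.5 agree with 13.7.2. One says eligible and evaluable, the other all treated; amending 13.1 alone would leave that difference in place.
3. List responses by disease, and state that no LCH-specific conclusion will be drawn from the pooled result.

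Sample size, assessments and data collection do not change. The downside is that the trial then offers no LCH-specific go/no-go.

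If the sponsor does intend an LCH endpoint, wording is not enough: 13.1 would need a number of LCH patients and a rule matched to it. At the planned 5 patients per year, 12 LCH patients would take 12/5 = 2.4 years only if every patient accrued had LCH.

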13.2 Sample Size, Accrual Rate and Study Duration

The planned accrual is 12 patients. The estimated accrual is 5 patients per year so we anticipate the accrual will occur over a 2 to 2.5 year period. Up to an additional 6 months of follow-up will be required on the last participant accrued to assess response. Thus the total study duration is anticipated to be 2.5 to 3 years.

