5.1 Treatment Regimen

For cycle 1, lenalidomide will be administered at a dose of 10 mg daily on days 1-21 of a 28 day cycle. Patients will be assessed for toxicity between days 22 and 28. If no grade 3 or greater toxicity has occurred the dose will be escalated to 25 mg daily on days 1-21 of a day 28 cycle (patients with a baseline CrCl of 30 to ≤ 60 will stay at the 10 mg dose). Patients with a baseline CrCl of 30 to ≤ 60 can be dose escalated to 25 mg if there is no grade 3 or greater toxicity at week 8 visit if CrCl has improved to >60. No dose escalated unless it is a toxicity due to neutropenia in which case the dose can be escalated if there is no recurrent neutropenia with growth factor support for two continuous cycles. Treatment will be administered on an outpatient basis. The maximum number of cycles is 12 (inclusive of cycle 1 and/or 2 dosing at 10 mg). Reported adverse events and potential risks are described in Section 7. Appropriate dose modifications are described in Section 6. No investigational or commercial agents or therapies other than those described below may be administered with the intent to treat the participant's malignancy.

Agent	Premedications; Precautions	Dose	Route	Schedule	Cycle Length
Lenalidomide	None	10 mg tablet (cycle 1)*	PO at approximately the same time each day(+/- 2 hours)	Days 1-21	28 days
Lenalidomide	None	25 mg tablet (cycle 2 and subsequent)*	PO at approximately the same time each day	Days 1-21	

The participant will be requested to maintain a medication diary of each dose of medication. The medication diary will be returned to clinic staff at the end of each cycle.

5.2 **Pre-Treatment Criteria**

5.2.1 Cycle 1, Day 1

Participants must meet all of the inclusion criteria, have none of the exclusion criteria, and must be registered to the protocol prior to initiating therapy.

The following studies and evaluations should be carefully reviewed to determine the patient's suitability to initiate study treatment.

- 1. Diagnosis of LCH, ECD, or HS is established by disease evaluations and laboratory studies and confirmed histologically
 - 2. Complete physical examination.
 - 3. Medical history: Detailed documentation of disease and treatment history with outcomes.
 - 4. Performance status $\geq 60\%$
 - 5. Concurrent medical conditions.
 - 6. Hematology: CBC with automated differential.

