5.2.2 Subsequent Cycles

A new course of treatment may begin on the scheduled Day 1 of a new cycle if:

- The ANC is \geq 1000/mm³;
- The platelet count is \geq 75,000 /mm³
- Any drug-related rash that may have occurred has resolved to \leq grade 1 severity
- Any other drug-related adverse events that may have occurred have resolved to \leq grade 2 severity.

If these conditions are not met on Day 1 of a new cycle, the subject will be evaluated weekly and a new cycle of treatment will not be initiated until the toxicity has resolved as described above. If a given toxicity has not resolved to an acceptable level within 28 days of the planned initiation of a cycle, the participant will be permanently removed from treatment.

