10. STUDY CALENDAR

Baseline evaluations are to be conducted within 1 week prior to start of protocol therapy. Scans and x-rays must be done \leq 4 weeks prior to the start of therapy. In the event that the participant's condition is deteriorating, laboratory evaluations should be repeated within 48 hours prior to initiation of the next cycle of therapy.

Assessments must be performed prior to administration of any study agent. Study assessments and agents should be administered within \pm 3 days of the protocol-specified date, unless otherwise noted.

	Pre- Study	C1 D1	C1 D15	C2 D1	C2 D15	C3 D1	C3 D15	C4 D1	C5 D1	C6 D1	C7 D1	C8 D1	C9 D1	C10 & 11 D1	C12 D1	Off Treatment ^l	Follow Up ^m
Lenalidomide		Х	Х	Х	Х	Х	Х	Х	Х	Х	Х	Х	Х	Х	Х		
Anticoagulation		Х	Х	Х	Х	Х	Х	Х	Х	Х	Х	Х	Х	Х	Х	X ^h	
Informed consent	Х																
Demographics	Х																
Medical history	Х																
Concurrent meds			Х														X
Physical exam	Х	Х	Х	Х		Х		Х		Х		Х	Х		Х	Х	Х
Vital signs ^a	Х	Х	Х	Х		Х		Х		Х		Х	Х		Х	Х	Х
Height	Х	Х	Х	Х		Х		Х		Х		Х	Х		Х		Х
Weight	Х	Х	Х	Х		Х		Х		Х		Х	Х		Х	Х	Х
Performance status	Х	Х		Х		Х		Х		Х		Х	Х		Х	Х	Х
CBC w/diff, plts	Х	$\mathbf{X}^{\mathbf{j}}$	Х	\mathbf{X}^{j}	X^k	Х	X^k	Х		Х		Х	Х		Х	Х	Х
Serum chemistry ^b	Х	Х	Х	Х	X^k	Х	X^k	Х		Х		Х	Х		Х	Х	Х
EKG	Х																
Bone marrow biopsy	\mathbf{X}^{i}																\mathbf{X}^{i}
Adverse event evaluation			Х														X
Tumor measurements ^c	Х					Х				Х			Х		Х	Х	Х
Radiologic evaluation ^d	Х					Х				х			Х		Х	х	Х
B-HCG ^e	X ^b	Х		Х		Х		Х		Х		Х	Х		Х		Х
Urine/ Plasma Assay for BRAF mutation ^f	Xe					Х				х					Х	Х	Х
Serum TNF-alpha ^g	Х					Х				X					Х	Х	Х

a: Temperature, BP, HR and O2 saturation by pulse oximetry at rest.

b: Albumin, alkaline phosphatase, total bilirubin, bicarbonate, BUN, calcium, chloride, creatinine, glucose, potassium, total protein, SGOT [AST], SGPT [ALT], sodium.

c: Tumor measurements are repeated at C3D1, C6D1, C9D1 and C12D1 and then every 3 months thereafter until month 24. After month 24 tumor assessments will occur every 6 months (+/- 2 weeks) until month 36 from treatment initiation. Documentation (preferably radiologic) must be provided for participants removed from study for progressive disease. A window of +/- 1 week is allowed prior to month 24 but tumor assessments must occur prior to dosing on the relevant cycle when active treatment is being administered

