13.5 Analysis of Primary Endpoints

The primary endpoint will be the proportion of responders. A responder is defined as an eligible, evaluable participant who achieves either complete resolution or regression of disease, per section 7, as the best overall response at any point during study therapy.

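### Section 13.2 allows up to 6 months to assess response in the last participant, but the primary endpoint runs over up to 12 cycles (11.0 months without delays) with 8-week maintenance

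*Combined protocol and SAP*

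**What the plan says.** - **Timeline (section 13.2).** Accrual of 12 patients at 5 per year is expected to take 2 to 2.5 years. Then: "Up to an additional 6 months of follow-up will be required on the last participant accrued to assess response". The conclusion drawn is: "Thus the total study duration is anticipated to be 2.5 to 3 years".
- **Primary endpoint (section 13.5).** A responder has complete resolution or regression "as the best overall response at any point during study therapy".
- **Length of therapy (sections 1 and 5.1).** Cycles are 28 days. "The maximum number of cycles is 12".
- **Delays (section 5.2.2).** A cycle may start late, and the participant leaves treatment for this reason only past a limit: "If a given toxicity has not resolved to an acceptable level within 28 days of the planned initiation of a cycle". The section does not limit how many cycles may be delayed.
- **Maintenance (section 11.1.2.3).** The "best response assignment will depend on the achievement of both measurement and confirmation criteria". Also: "Responses should be maintained for at least 8 weeks".
- **Scans (section 10, footnote c).** "Tumor measurements are repeated at C3D1, C6D1, C9D1 and C12D1 and then every 3 months thereafter until month 24". A window of one week either side applies before month 24.
- **Denominator and rule (sections 11.1, 13.7.2, 13.1).** Everyone who takes one dose is assessed for response. Three responses in 12 make the treatment worth further study.
- **Maturity (section 14).** The end of the study is either the point when the last data items are due or the point when outcome data are mature enough to analyse. For the second it refers the reader to section 13.2.

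**The concern.** The 6 months is worded as a maximum and as what is needed to assess response. A last participant who receives the full course is still on therapy, and can still become a responder, for about five months after that. The 2.5 to 3 year total inherits the same input.

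No other passage times the primary analysis, so 13.2 is the plan's only statement of when the response data are ready. If the analysis were done 6 months after the last enrolment, participants with unfinished assessment would stay in the denominator without a response to their name. That can only lower the number of responders. The decision turns on 3 of 12, so one missed responder could change whether a larger trial is proposed.

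**Working it through.** Conversion: 365.25/12 = 30.44 days per month. Time runs from C1D1 of the last participant. Any gap between enrolment and C1D1 would only add to it.

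**1. The plan's own figure.** Accrual is 12/5 = 2.4 years, inside the stated 2 to 2.5. Adding 0.5 year gives 2.0 + 0.5 = 2.5 to 2.5 + 0.5 = 3.0 years, as stated. The addition is right. The question is the 6-month input.

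**2. Length of therapy.** 12 x 28 = 336 days; 336/30.44 = 11.04 months. With one 28-day delay, 336 + 28 = 364 days = 11.96 months.

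**3. What is known at 6 months.** 6 x 30.44 = 182.6 days, and 182.6/28 = 6.5, so the participant is in cycle 7. Cycle c day 1 falls (c - 1) x 28 days after C1D1:

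| First seen at | Day | Months | Day 8 weeks is reached | Next scheduled scan that can show it |
|---|---|---|---|---|
| C3D1 | 56 | 1.84 | 112 | C6D1, day 140 |
| C6D1 | 140 | 4.60 | 196 | C9D1, day 224 |
| C9D1 | 224 | 7.36 | 280 | C12D1, day 308 |
| C12D1 | 308 | 10.12 | 364 | after therapy |

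Only C3D1 and C6D1 fall before day 183. A response first seen at C6D1 reaches 8 weeks on day 196. With the earliest scan the window allows, this is 133 + 56 = day 189, and the next scan is on day 217. All of these are later than day 183. So at 6 months only a response first seen at C3D1 can have been shown to last.

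**4. A response first seen at C12D1.** The last dose (C12D21) is on day 11 x 28 + 20 = 328. The off-treatment visit is within 7 days of it, on days 321 to 335. That is 13 to 27 days after C12D1, or at most 335 - 301 = 34 days if the C12D1 scan was a week early. This is under 56 days, so 8-week maintenance cannot be shown before the first follow-up scan.

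**5. Time actually needed, without delays.**
- Maintenance shown on therapy: to the end of cycle 12, 11.04 months, about 5 months more than stated.
- Maintenance may be shown after therapy: the next scan is 3 months after C12D1 (10.12 + 3 = 13.12 months) or 3 months after the last dose (10.78 + 3 = 13.78 months, or 14.24 with the 2-week window). That is 7.1 to 8.2 months more than stated.

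**6. Effect on the total.** 336/365.25 = 0.92 year. The last participant's therapy ends at 2.0 + 0.92 = 2.92 years, 2.4 + 0.92 = 3.32 years or 2.5 + 0.92 = 3.42 years, depending on accrual.

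**The case against.** The strongest reply is that 13.2 is a forecast and not an analysis rule. Its accrual and duration figures are offered as estimates. The responder definition, the evaluable set and the 3-of-12 rule do not use the 6 months. Scans continue through C12D1 and on to month 36, and section 14 allows 24 months after the end of the study to release results. A team that follows 13.5 would count late responses. Participants who progress or stop early also need less time, and if accrual takes 2.0 years with no delays, therapy ends at 2.92 years, inside the stated range.

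Most of this stands, and it limits the harm. It does not rescue the figure. The sentence says what is required to assess response, the total is derived from it, and section 14 refers to it for data maturity. Reading the 8-week rule as advice does not help either, because the 11.0-month therapy window alone exceeds 6 months.

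Three stronger readings are tempting, but the documents do not support them:
- **That the plan orders an analysis at 6 months and will undercount responders.** No passage orders one, and section 14 offers a second end-of-study definition that does not use 13.2.
- **That the loss in the chance of reaching 3 of 12 can be stated.** That needs a true response rate, the timing of responses and the spacing of enrolments and delays. The plan gives none of these in usable form.
- **That the 36-month follow-up contradicts the 2.5 to 3 year total.** Section 13.2 ties that total to assessing response, so this is at most a separate matter of labelling.

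**Conclusion.** Wrong as written. The 6 months in section 13.2 cannot cover the endpoint defined in 13.5 and 11.1.2.3 for a last participant who stays on treatment. The shortfall is about 5 months if maintenance must be shown on therapy and about 7 to 8 months if it may be shown afterwards. Both figures assume no treatment delays, and each delay that moves the later cycles adds to them. At the plan's own accrual of 2.4 years, therapy for the last participant ends at about 3.3 years, past the 3-year upper end. At 2.0 years it still fits.

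The consequence for the result is conditional. Section 14 permits, but does not order, an analysis on 13.2's date. If one were done then, the error could only go one way, towards fewer responders. The sample size and the 3-of-12 rule are unaffected.

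**What to change.** 1. In section 13.2, replace the 6-month figure with an event-driven rule, for example: *The primary analysis will be done when every treated participant has completed or stopped lenalidomide and has had the scheduled assessment needed to judge 8-week maintenance, or has progressed, died or left the study.*
2. In section 13.5, state whether maintenance may be shown at a scan after therapy ends. The first item cannot be applied without this. If it may not, say that a response first seen at C12D1 cannot qualify.
3. Restate the anticipated time to the primary result, marked as assuming no treatment delays: at least about 11 months after the last enrolment if maintenance must be shown on therapy, or at least about 13 to 14 months if it may be shown later. Adjust the total to match.

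The cost is wording, plus a stated time to the primary result that is longer by about 5 months (on therapy) or 7 to 8 months (later), and more with delays. All the scans are already in the study calendar, so no visits or scans are added.
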